## 6.9 Safety Assessments

### Adverse Events

Adverse events will be reported by the subject (or, when appropriate, by a caregiver, surrogate, or the subject's legally acceptable representative) from the time of giving written informed consent through to completion of subject participation, including the follow-up period (28 days post Visit 5). Adverse events will be followed by the investigator for a length of time as determined by the sponsor. Specific details on adverse event reporting are provided in section 8 "Safety Assessment".

## 7 STATISTICAL CONSIDERATIONS

### 7.1 Overview

This two year (approximately), multi-centre, prospective, observational study is designed to collect clinical data on the real-world use of Akynzeo® in Canada. The aim of the study is to support clinical data from the development program by the generation of real world evidence on the effectiveness, safety and additional parameters of Akynzeo® in a local clinical setting.

This study will enroll adult male or female chemotherapy patients of various cancer types who are scheduled to receive chemotherapy with high emetogenic potential for a maximum of 2 days. Akynzeo® (netupitant/palonosetron) will be used for the prevention of nausea and vomiting in oncology patients receiving HEC.

The primary study objective is to generate RWE on the quality of life by means of the FLIE questionnaire.

### 7.2 Sample Size Determination

The study is to include up to 200 patients. No formal sample size calculation has been carried out. The planned number of patients to be enrolled in the study should be adequate for the exploratory purposes and allow a conclusion to be drawn regarding the use of Akynzeo® in real life in Canada.

### 7.3 Efficacy and Safety Analysis

This is a two year (approximately), multi-centre, prospective, observational study designed to collect clinical data on the real-world use of Akynzeo® in Canada. All analyses will be descriptive in nature.

Before beginning data analysis, plausibility checks will be performed. Implausible or ambiguous data will be excluded from analysis.

Prior to database lock, a statistical analysis plan (SAP) defining all details of analysis will be prepared. A table mock-up (TMU) document which will illustrate the details of presentation and analysis for data collected in this study will accompany this document.

The Intent-To-Treat (ITT) population includes all patients who were entered into the study web-based application and have a date of signed informed consent available. This population will be used to provide descriptives for patients enrolled by centre, patient disposition and reasons for screen failure.

The modified Intent-To-Treat (mITT) population includes all patients who were included in the ITT population and fulfilled all entry criteria and received at least one dose of the study treatment (Akynzeo®). Missing questionnaires/assessments will not be imputed. The mITT population will be used for the analysis of the primary, secondary and exploratory endpoints not including health resource utilisation (ER visits, hospitalizations). This population will also be used for demographic, medical history and concomitant medication tables.

The Safety population includes all patients who received at least one dose of the study treatment (Akynzeo®). This population will be used for all safety analyses and health resource utilisation (ER visits, hospitalizations) tables.

Continuous variables will be summarized descriptively by number of observations, number of missing observations, mean, standard deviation, median, 1st quartile, 3rd quartile, minimum and maximum. Categorical variables will be summarized descriptively as frequency counts and percentages.

A number of p-values may be presented in the reported tables for exploratory purposes. Statistical testing will be performed at the two-sided 0.05 significance level unless otherwise specified. P-values will not be adjusted for multiple comparisons.

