## 2.2 Secondary Outcomes

The response to Akynzeo® and the necessity for use of a rescue medication will be recorded to evaluate effectiveness. The medicinal products used as rescue medication will also be recorded. The following parameters will be calculated from information recorded in the patient diary:

- Complete Response (CR): no emetic episode and no use of rescue medication in the overall period (0-120h/Day 1-5)
- Severity of nausea (daily from Day 1 to Day 5) using a VAS scale (Visual Analogue Scale)
- Time to failure (time to first emetic episode or time to rescue)
- Use of rescue medication (daily from Day 1 to Day 5)

The collection of safety data and adverse events AEs in connection with administration of Akynzeo® will be performed.

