**2. Have you experienced any vomiting in the last 24 hours?**

- No
- Yes → Please record on the Retching and/or Vomiting page (page 12).

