**RESCUE MEDICATION**

	Did you take medication for the treatment of nausea and/or vomiting during the 120 hours (5 days) after the start of chemotherapy?	Yes  No 
--	-------------------------------------------------------------------------------------------------------------------------------------------	-------------------------------------------------------------

- *If you checked "Yes", please record every medication you take for the treatment of nausea and/or vomiting during the 120 hours (5 days) after the start of chemotherapy.*
- *Please record the date and time taken in the most precise manner.*
- *For each medication taken, please record the dose, route and quantity.*

Medication <small>Please list every administration of medication separately</small>	Dose <small>(e.g., 10 mg)</small>	Route <small>(e.g., oral, rectal, topical, intravenous)</small>	Quantity <small>(e.g., 1 tablet)</small>	Date and Time of Intake of Medication <small>Please record the date and time of each medication taken.</small> <small>(00:00 – 23:59)</small>	
Prochlorperazine	10 mg	Oral	1 tablet	01 / Jun / 2018	10 : 25
The first row is pre-filled as an example.				 /  / 	 : 
				 /  / 	 : 
				 /  / 	 : 
				 /  / 	 : 
				 /  / 	 : 

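### Section 7.3 excludes implausible or ambiguous data with no criteria, which is likely, though not certain, to favour complete response, rescue use and time to failure

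*Combined protocol and SAP*

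**What the plan says.** Section 7.3 (Efficacy and Safety Analysis) sets two steps: "Before beginning data analysis, plausibility checks will be performed", and then "Implausible or ambiguous data will be excluded from analysis". Neither is developed. The section names no criteria, unit of exclusion, decision maker, listing of exclusions or sensitivity analysis. It also says "Missing questionnaires/assessments will not be imputed". Further detail is left to a SAP due before database lock; that SAP is not in the supplied text.

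Section 2.2 (Secondary Outcomes) says of the effectiveness outcomes that "The following parameters will be calculated from information recorded in the patient diary", and defines the main one as "Complete Response (CR): no emetic episode and no use of rescue medication in the overall period". No scoring algorithm is given.

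The diary (Appendix 2) records events in three ways:
- On each of Days 1 to 5 there is a No/Yes item, "Have you experienced any vomiting in the last 24 hours", and a No/Yes item on medication taken because of severe nausea.
- Each of the two logs (retching/vomiting, and rescue medication) opens with a Yes/No box for the whole 120 hours.
- Below each box are rows for individual events: date, onset and end time for emesis; drug, dose, route, quantity, date and time for medication. The rescue log asks: "Please record the date and time taken in the most precise manner".

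**The concern.** An exclusion rule is neutral only if responders and failures are equally exposed to it. Here they probably are not. The handwritten rows carry the dates, times, drug names and doses that a plausibility check examines, and a patient with nothing to log leaves them blank.

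The daily items are also narrower than the logs. The daily page asks about vomiting, while the log also takes retching. The daily page asks about medication for severe nausea, while the log takes any drug used to treat nausea or vomiting. A patient who took rescue for moderate nausea, or who only retched, can truthfully answer No on the daily page and Yes in the log. That record looks ambiguous, yet it holds a logged event. An event-free patient who answers correctly says No throughout and cannot produce this conflict.

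At stake are complete response, rescue use and time to failure, all secondary endpoints in Section 3.5. The study has a single arm and no blinding is described. The SAP is required only before database lock, so the protocol does not prevent the exclusion criteria from being settled after outcomes are visible.

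**Working it through.** The plan gives no complete response rate, exclusion count or sample size calculation, so there is no figure of its own to reproduce. The check is by direct counting.

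**Inputs**
- N = 200, the planned maximum (Sections 3.3 and 7.2).
- Base rate: 74.3% overall complete response in the NEPA arm of the AC phase III trial (Section 1.4, Study 2). Using it for this study is an assumption. In whole patients, R = 149 responders and F = 51 failures, 149/200 = 74.5%.
- Range for the base: 60% (assumed) to 89.6% (Section 1.4, Study 1, 300 mg group; 179/200 = 89.5%).
- k = number of patients whose cycle is judged ambiguous. The documents give no rate; 5, 10 and 20 are assumptions.

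**Three readings of exclusion**

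(a) The sole event row is deleted and the cycle is read as event-free: (R + k)/N.
- k = 5: 154/200 = 77.0%
- k = 10: 159/200 = 79.5%
- k = 20: 169/200 = 84.5%

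(b) The row is deleted but a Yes in the log box or on a daily page is kept: R/N = 74.5% for every k. Deleting one of several rows likewise leaves complete response unchanged, although losing the earliest row lengthens time to failure.

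(c) The cycle is set to missing, with r responders and f failures excluded: (R − r)/(N − r − f). This rises only if f/(r + f) exceeds F/N = 51/200 = 25.5%.
- k = 10, all failures: 149/190 = 78.4%
- k = 10, half failures: 144/190 = 75.8%
- k = 10, in proportion: 74.5%
- k = 10, all responders: 139/190 = 73.2%
- k = 20, all failures: 149/180 = 82.8%
- k = 20, all responders: 129/180 = 71.7%

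**Other base rates, k = 10**
- Base 60.0%: (a) 130/200 = 65.0%; (c) from 110/190 = 57.9% to 120/190 = 63.2%; break-even 40.0%.
- Base 89.5%: (a) 189/200 = 94.5%; (c) from 169/190 = 88.9% to 179/190 = 94.2%; break-even 10.5%.

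**Scale.** The 95% half-width at 74.5% and N = 200 is 1.96 × √(0.745 × 0.255/200) = 6.0 points. The shift under (a) with k = 10 is 79.5 − 74.5 = 5.0 points, close to the full sampling uncertainty.

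Section 7.3 does not say which of (a), (b) or (c) applies. The no-imputation sentence points towards (c) for whole missing assessments, but does not say whether a cycle that has lost a row is missing or event-free.

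**The case against.** A reader might infer that complete response is simply the absence of event rows, so that the rule can only push it up. The documents do not support that. Event-free patients also leave records: ten daily answers (two items on five days) and two log boxes per cycle, with an instruction to tick No when there was no retching or vomiting. Any of these can be blank or mis-ticked, and excluding such cycles lowers the rate, as the 71.7% figure shows. Some exclusions would also be correct, such as an entry outside 0–120 h, or scheduled Day 2–4 dexamethasone (Section 5.1) written in the rescue log. This part of the objection stands and limits the claim to a likely direction.

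A reader might also infer that the primary endpoint, the cycle 1 FLIE total score (Section 3.4), is biased or can be altered without trace. That does not follow. FLIE items run in opposite directions (Appendix 3), so odd-looking forms are foreseeable, but the event-row argument does not reach them, no direction is shown, and Section 7.3 reports the number of missing observations for continuous variables.

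There are controls. Study personnel review the diary with the patient (Appendix 2), entries are validated online and physicians must supply background when errors are suspected (Section 12.4), and monitors verify against source (Section 13.1). These reduce the number of unresolved entries. They do not change what Section 7.3 prescribes for those that remain. The SAP may supply criteria, but that cannot be judged here.

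Finally, whether a retching-only patient is a failure depends on whether retching is an emetic episode, which Sections 2.2 and 3.5 leave open. The rescue mismatch does not depend on that.

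**Conclusion.** The point holds as a likely, not certain, bias in favour of the product on three secondary endpoints. Section 7.3 states a rule rather than merely omitting a detail, and the fields most open to it belong mainly to patients with logged events. Under reading (c) the bias is upward once failures exceed 25.5% of exclusions at a base of 74.5%; the structure of the diary makes that plausible but does not prove it. With 10 such failures in 200, complete response moves from 74.5% to 79.5% under (a) or 78.4% under (c), and not at all under (b). These sizes rest on an assumed base rate, an assumed number of ambiguous records, and failures being the ones affected. They illustrate the exposure and do not predict the result.

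**What to change.** Replace the exclusion sentence in Section 7.3, and carry the detail into the SAP, so that:
- implausible or ambiguous entries are queried, and unresolved ones are kept;
- a logged emetic or rescue entry counts as an event even if its time or dose is unclear, unless shown to lie outside 0–120 h or to be scheduled prophylaxis rather than rescue;
- a cycle with an excluded event row is never scored as a complete response;
- the SAP states how daily items, log boxes and rows combine, including whether retching counts as an emetic episode;
- event-free cycles with missing pages are reported as missing, with bounds, so that the rule does not push the rate down instead;
- any exclusion is decided before outcome tables are run and is listed with its reason and count;
- endpoint tables are repeated with nothing excluded.

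The cost is a few sentences, one extra table run and possibly a slightly lower complete response rate. It should be done before database lock; afterwards the choices can no longer be shown to be independent of the outcome.

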## 8 SAFETY ASSESSMENTS

Timely, accurate, and complete reporting and analysis of safety information from clinical studies are crucial for the protection of subjects, investigators, and the sponsor, and are mandated by regulatory agencies worldwide. Adverse events will be collected from the time a subject has signed an ICF and followed until the end of study-visit 6 (28 days post visit 5/last dose of Akynzeo®).

### 8.1 Adverse Event Definitions

According to the currently valid Directive of the European Parliament and of the Council relating to the implementation of good clinical practice in the conduct of clinical studies on medicinal products for human use (2001/20/EC), an adverse event (AE) is “Any untoward medical occurrence in a patient or clinical study subject administered a medicinal product and which does not necessarily have a causal relationship with this treatment”. An AE could therefore be any unfavourable or unintended sign (for example, an abnormal laboratory finding), symptom or any disorder with a temporal relationship to the use of a medicinal product, regardless of whether or not it is considered to be related to use of the medicinal product.

In the context of this study, all adverse events (AEs) from the time of Akynzeo® administration over a period of 5 days during the chemotherapy cycles which are part of the observation period will be documented on the appropriate pages of the eCRF.

A serious adverse event (SAE) is defined as an AE that:

- results in death;
- is life-threatening;
- requires hospitalization or prolongation of existing hospitalization;
- results in persistent or significant disability or incapacity;

---

 This includes every AE that – in the opinion of the investigator – is life-threatening for the study subject. This definition does not include events that may have led to death, if they had occurred in a more severe form.

- is a congenital anomaly or results in a birth defect or
- significant medical events that may endanger patients or require an intervention to prevent the above characteristics or consequences.

An unexpected adverse event is any event for which, with regard to its nature, severity or incidence, no details have been included to date in the current Product Monograph for Akynzeo®. The assessment of the "expectedness" of an AE is performed by the sponsor.

Planned surgical interventions or hospitalizations scheduled before the informed consent form was signed but carried out during the study period (study procedures, chemotherapy cycles, etc.) are not to be regarded as (serious) AEs.

The investigator assesses whether or not an event qualifies as a serious adverse event (SAE, see criteria above).

If an adverse event is classified as serious and there is at least reasonable possibility of a causal relationship to the administration of Akynzeo®, this represents a serious adverse drug reaction (SADR).

All information on Special Situations from the time of Akynzeo® administration will be documented on the appropriate pages of the CRF and transcribed to the AE pages of the eCRF.

Special situations consist of the following:

- exposure during pregnancy, embryo/foetal maternal or paternal exposure (even if uneventful),
- lack of efficacy\*,
- off-label use,
- overdose,
- occupational exposure,
- misuse or abuse (symptomatic or not),
- medication errors,
- transmission of infectious agent

\*refer to Section 10 for definition of lack of efficacy

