## 3 STUDY DESIGN

### 3.1 Study Overview

This two year (approximately), multi-centre, prospective, observational real-world study is designed to collect data on the use of Akynzeo® (netupitant/palonosetron) for the prevention of nausea and vomiting in oncology patients receiving highly emetogenic chemotherapy (HEC).

The visit schedule is comprised of 6 study visits (Table 1):

- Visit 1/Screening (4 weeks to 0 weeks prior to Visit 2)
- Visit 2: (Day of/but prior to 1st chemotherapy treatment administration)

- Visit 3: (Day of/but prior to 2nd chemotherapy treatment administration)
- Visit 4: (Day of/but prior to 3rd, chemotherapy treatment administration)
- Visit 5: (Day of/but prior to 4th, chemotherapy treatment administration)
- Visit 6/Final Visit

Visit 1 and 2 can be combined as determined by the investigator. Patients will report the daily occurrence and intensity of nausea and vomiting, rescue medications, adverse events (excluding nausea and vomiting) in a diary from Day 1 (chemotherapy treatment day) to Day 5/time point 0-120 hours post chemotherapy administration of each observation period.

Safety events occurring between chemotherapy cycles will be reported by the patient. Patient will have a follow up period of 28 days post the last-chemotherapy cycle.

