### 3.7 Safety Assessment

Safety will be evaluated by the incidence and type of adverse events (AEs), serious adverse events (SAEs) and AEs leading to discontinuation of treatment in all patients.

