## **8.3 Adverse Event Reporting**

Safety Data Collection:

Should the patient experience any AEs or Special Situations and report these to the investigator during a visit, the investigator will enter all the information available directly into the EDC system within 24 hours. Investigator shall perform a causality assessment (related/not related to CINV prophylaxis/treatment) for each AE. The AE Report Form (Appendix 6a) displays the information that the Investigator is initially required to provide. Investigator's assessment of relatedness to medicinal product for which sponsor is MAH or distributor is included in Appendix 6. Information on related and non-related Serious AEs, Special Situations and Akynzeo® related non-serious AEs will be included on the specified safety report forms (Appendix 6b & 6c).

The Global Reporting Form for SAEs/AESIs/Special Situations and the Akynzeo®-Related Non-Serious Adverse Event Forms will be directed to the sponsor's pharmacovigilance address ([[contact]](mailto:[contact])), where the report will be processed by the sponsor's pharmacovigilance team. An Akynzeo®-related AE that does not meet a seriousness criterion shall be sent by the Investigator to the Sponsor email address ([[contact]](mailto:[contact])) within 2 calendar days from Day 0 (investigator adverse event first awareness date). Serious AE, either related or non-related and Special Situations, shall be sent within 24 hours of their detection.

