Appendix 6: Safety Reporting Forms

6a. Adverse Event Reporting Form

	Adverse Events CAN-PRO-NEPA-001 Case Report Form	
 
 				-					
 
 Site Number		Patient Number	
 
					-					Site Number					Patient Number			
				-																
Site Number					Patient Number															

1. Please complete all fields for each adverse event.

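### Section 8.1 ties eCRF documentation of adverse events to the 5 days after each Akynzeo dose, while Sections 3.1, 6.9, 8 and 8.3 cover the whole study; the end of follow-up is also stated inconsistently.

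*Combined protocol and SAP*

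**What the plan says.** Section 3.7 makes adverse events the safety evaluation: "Safety will be evaluated by the incidence and type of adverse events (AEs"), together with serious events and events leading to discontinuation. The period over which they are recorded is described in several places.

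- **Section 8.1** has the eCRF document "all adverse events (AEs) from the time of Akynzeo® administration over a period of 5 days during the chemotherapy cycles" that belong to the observation period.
- **Section 6.9** has events reported "from the time of giving written informed consent through to completion of subject participation, including the follow-up period (28 days post Visit 5"), and leaves the length of follow-up of events to the sponsor.
- **Section 8** starts at signature of the consent form, with events "followed until the end of study-visit 6 (28 days post visit 5/last dose of Akynzeo").
- **Section 3.1** adds that "Safety events occurring between chemotherapy cycles will be reported by the patient", and that "Patient will have a follow up period of 28 days post the last-chemotherapy cycle".
- **Section 8.3** says that, for an event reported at a visit, "the investigator will enter all the information available directly into the EDC system within 24 hours". It names no window.
- **Appendix 6a**, the adverse event form, instructs "Please complete all fields for each adverse event", also without a window.
- **Table 1** puts Visit 6 within 28 days of cycle 4 or before the next cycle starts. **Section 6.6** puts it before the next cycle. Table 1 schedules adverse event assessment at Visits 2 to 6.
- **Section 4.4** requires the Final Visit assessments at early exit and ends data collection at that visit.

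**The concern.** The two recording rules differ at both ends. The 8.1 window opens at dosing and closes 5 days later, once per cycle. The 6.9 and 8 window opens at consent and runs without gaps to the end of participation. If some sites work from one and some from the other, a single incidence table mixes patients observed for a few days per cycle with patients observed continuously, and incidence is understated at the sites that follow 8.1. Section 7.3 gives no adverse event window and leaves the details to a SAP prepared before database lock. A SAP can narrow a complete data set, but it cannot restore events that were never entered.

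The unsettled end of follow-up raises the same problem on a smaller scale: patients contribute different observation time after the last observed dose, depending on which section the site applied.

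**Working it through.** The plan states no figure to reproduce, and Section 7.2 says that no formal sample size calculation was done. The check compares the passages and then counts days.

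**1. Can 8.1 be reconciled with 6.9 and 8?** The natural attempt is that 6.9 and 8 govern what is collected while 8.1 governs what goes on the eCRF. Section 8.3 defeats this, because it sends any event reported at a visit straight into the EDC system without a 5-day limit. The form in Appendix 6a has no such limit either.

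**2. What would be left off the eCRF?** Section 8.3 sends all serious events (related or not) and Special Situations to the sponsor within 24 hours, and Akynzeo-related non-serious events within 2 calendar days, with no 5-day limit. What remains exposed is mainly non-serious events judged unrelated that start outside the windows.

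**3. How much time does the 8.1 window cover?** Inputs: 4 observed cycles, 5 days each (8.1), and 28 days after Visit 5 (6.9). Cycle length c is not in the documents; 21 and 28 days are assumed.

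- 8.1 window: 4 × 5 = 20 days.
- First dose (Visit 2) to 28 days after Visit 5: 3c + 28.
- c = 21: 63 + 28 = 91 days; 20/91 = 22.0%.
- c = 28: 84 + 28 = 112 days; 20/112 = 17.9%.

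The screening period of up to 28 days, which 6.9 and 8 also cover, is not counted. A 14-day cycle is left out of this step because it fits poorly with the 4 to 6 months of observation per subject in the Synopsis. Even with full screening it gives 28 + (42 + 28) = 98 days, against about 122 days for 4 months. The same sum gives 119 days for 21-day cycles and 140 days for 28-day cycles.

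**4. Does Visit 6 equal 28 days after Visit 5?** Visit 5 is Day 1 of cycle 4. If Visit 6 precedes the next cycle, it comes no later than about c days after Visit 5, so the shortfall is at least about 28 − c.

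| Assumed cycle | Latest Visit 6, days after Visit 5 | Shortfall against 28 days |
|---|---|---|
| 14 days | 14 | 14 |
| 21 days | 21 | 7 |
| 28 days | 28 | 0 |

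This applies to patients who go on to a further cycle.

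**5. What of a patient who stops before cycle 4?** There is no Visit 5, so the anchor in 6.9 does not exist. Section 8 offers the last dose as a second anchor. Section 4.4 ends data collection at the early termination visit, which may come earlier than 28 days after that dose, while 6.9 has events followed for a time set by the sponsor.

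**The case against.** The best defence is that 8.1 does not say that only these events are documented. A site that records everything from consent onward breaches nothing in 8.1, and the longer window has more support in the document, so the 5-day sentence is probably a stray. That is fair, and it is why the practical effect may be nil. It does not make the sentence harmless. 8.1 is current text, is framed as a rule for this study, and names a period for eCRF entry that serves no purpose if the whole study is already covered. Staff working from 8.1 could reasonably take it as the limit.

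A second defence is that early stoppers are largely handled: 4.4 requires the Final Visit assessments, which include adverse events, and follow-up in 6.9 may mean pursuing known events to their outcome. This narrows the point, but the document does not say so, and 4.4 taken literally bars even that.

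Several stronger readings are tempting but unsupported:

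- **Serious or drug-related events would be lost.** They would not; the reporting duties in 8.3 carry no 5-day limit.
- **The follow-up statements spread over a further full 28 days.** This needs the 3.1 follow-up to run from the end of cycle 4. The Synopsis and the Table 1 footnote time the period after a cycle from chemotherapy administration. On that usage, 3.1 agrees with 6.9 for a patient with four cycles.
- **About 50 of 200 patients would lack Visit 5**, from the 75% who completed four cycles in Study 3 (Section 1.4). That rate counts completion of cycle 4, whereas Visit 5 is its first day, and 76% of that population received moderately emetogenic chemotherapy.
- **The patient diary has no adverse event page.** Appendix 2 shows none, but it refers to two pages for each log and shows one, so it may be abridged.

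**Conclusion.** The inconsistency is real and the text should be corrected. As written, 8.1 and the other sections give sites different rules for what enters the eCRF, and the affected quantity is the adverse event incidence named in 3.7. The bias, if any, is downward and falls mainly on non-serious events judged unrelated to Akynzeo.

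The 22% and 18% figures rest on assumed cycle lengths. A reader might infer that some four-fifths of events would be missed. The documents give no distribution of onset times, so that does not follow. The loss is zero if all events start within 5 days of a dose, or if sites follow 6.9, 8 and 8.3.

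The end of follow-up is a smaller, separate fault. Equating Visit 6 with 28 days after Visit 5 fails by at least about 7 days for a 21-day cycle, by 14 for a 14-day cycle, and not at all for a 28-day cycle. The 6.9 anchor is missing for anyone who never reaches Visit 5. The documents do not allow an estimate of how many patients that is.

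**What to change.** - Align the 5-day sentence in Section 8.1 with the adverse event window in Sections 6.9 and 8.
- State one end of adverse event follow-up and use it in Table 1 and Sections 3.1, 6.6, 6.9 and 8, with an anchor that also exists for patients without a Visit 5.
- Reconcile Section 4.4 with Section 6.9 on adverse event data after early termination. This review does not say which should prevail.

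The cost is a protocol amendment with REB review (Section 11.1) at up to 20 sites. No visits are added, since adverse events are already assessed at Visits 2 to 6. Reported incidence may rise slightly, through fuller entry at any site that had followed 8.1 literally.
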